3.4 Participant Withdrawal

- The PI can withdraw participants if the PI determines the participants have sustained any injury or complication that prevents them from continuing with the study.
- The PI can withdraw participant if the participant is considered not a candidate for chemoradiation treatment after radiation and/or medical oncology consult.
- Participants can voluntarily withdraw from the study at any time.

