5.2.7 Treatment Interruption (12/6/15)

If a grade 3 hematologic toxicity (ANC or platelets) develops during chemoradiotherapy, all treatment (both radiation and chemotherapy) should be discontinued for a minimum of 1 week.

Treatment may be resumed when the hematologic toxicity resolves to \leq grade 2. If these laboratory values have not been reached after a 1-week delay, they should be checked weekly until they become acceptable. If after 3 weeks the blood counts have not recovered, all protocol treatment should be discontinued and the patients should be treated on an individual basis.

For a grade 3 acute colitis, cystitis, or any other grade 3 infield (radiation-related) toxicity during any treatment week, treatment should be delayed until the toxicity subsides to the grade 2 level. If the delay is greater than 3 weeks, then the patient should be considered intolerant of protocol therapy and appropriate off-protocol therapy given.

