5.3 DRUG THERAPY

Medical Oncologist will determine the chemotherapy regimen concurrently used with radiation as a radiation sensitizer. The following is a list of chemotherapeutic drugs that could be used per NCCN guideline:

Cisplatin

Cisplatin and 5-FU

5-FU and Mitomycin

Cisplatin and Paclitaxel

Low dose gemcitabine

All AE occur during the study period will be assessed and attribution assigned.

6. Post-Induction Response Evaluation (for Chemoradiation Arm only)

Following the completion of induction chemoradiotherapy and the evaluation of response all patients must be re-registered via cystoscopy and biopsy. At this time, the response results (biopsy results and cytology results) and the second phase of the treatment (i.e. radical cystectomy for tumor response $T \geq 1$ or consolidation chemoradiotherapy for tumor response T0, Ta, and Tcis) will be recorded and a new data collection calendar generated. Details regarding “Radical Cystectomy” can be found at Section 5.1. Details regarding “Consolidation Chemoradiotherapy” can be found at Section 5.2.2.

The following information will be supplied:

- original case number
- results of evaluation and pathologic T stage
- treatment start date (radical cystectomy or consolidation chemoradiotherapy)

The treatment option registered and the new data collection calendar will be based on the parameters specified by the protocol. If the investigator or the patient deviates from the protocol specified treatment, documentation of this and data submission as outlined in our study Standard operating procedure.

Patients who have developed distant metastases during the induction phase of treatment and who will not continue therapy will remain on the original calendar schedule for continued follow up only.

After completing either radical cystectomy or consolidation chemoradiotherapy, all response results to the second phase of treatment (i.e., either pathologic staging from the radical cystectomy or cystoscopic re-evaluation performed following completion of consolidation chemoradiotherapy) will be promptly submitted to Data Management.

7. 1 Post-Treatment Study Visits at 3, 6, 9, 12, 18, 24, 30, and 36 month \pm 1 month

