7.2 Withdraw Visit

Whenever possible, participant will be scheduled for a withdraw visit if she/he chooses to withdraw from the study early or if the PI needs to withdraw the participant from the study. This is an optional visit. During this visit, participant will be asked to have research blood draw and complete study questionnaires. Reasons for withdraw will also be asked and recorded. Participant will have the choice to partake any or all of the activities during withdraw visit.

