9. DATA COLLECTION & STUDY EVALUATIONS

Medical records will be reviewed prior to “Baseline Study Visit” to confirm study eligibility. After obtaining consent, socio-demographic data will be collected through chart review and interviews. Clinical data that will be collected include but not limited to bladder cancer treatment history, tumor characteristics, stage, laboratory results, medications and co-morbidity.

Study team member or clinic staff will measure height, weight, and vital signs at each specific study time point. Research blood will be drawn at each study time point. Blood and tissue samples may be banked under the optional study (HSC20050234H GU Tissue Bank). For those participants who declined to participate in the optional study, any leftover samples will be permanently de-identified through the GU Tissue Bank (HSC20050234H) honest broker system. At the close of this study, all biological materials collected will be rolled into HSC20050234 GU Tissue Bank.

9.1 Feasibility: We will report recruitment, visit dates, adherence, attrition rates and compliance with randomization for each arm of the study

9.2 Bladder-intact survival: We will report proportion of patients who failed chemoradiation and required salvage cystectomy

9.3 Quality of life: A self-assessment questionnaire using the European Organization for Research and Treatment of Cancer (EORTC) QLQ- C30 and FACT-Bladder will be used for QOL assessment at baseline, 3, 6, 9 and 12 months.⁸

9.4 Progression free survival: This will be measured from the date of finishing chemoradiation or radical cystectomy to the date of first documentation of progression. Progression will be determined using RECIST 1.1 criteria by the treating physician based on radiographic or pathologic evidence of disease progression, or death from disease. Any documented recurrence will be considered progression.⁹ The date of progression will be recorded.

9.5 Candidate gene expression analysis: For the participants who have consented to be part of the optional study (“GU Tissue Bank HSC20050234H), a microarray analysis will be performed on all bladder tumor specimens using Agilent Technologies (Agilent SurePrint G3 Human Gene Expression 8x60K v2) Microarray. Goal is to study the landscape of 50 important candidate genes, which are involved in bladder cancer (for example-BRAF, KRAS, EGFR, FGFR).

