Adverse Event Definition: An adverse event (AE) is defined as any untoward or unfavorable medical occurrence in a human subject, including any abnormal sign (for example, abnormal physical exam or laboratory finding), symptom, or disease, temporally associated with the subject's participation in the research, whether or not considered related to the subject's participation in the research. For this study, all adverse events will be documented starting with the date of study enrollment and ending 30 days after the "12 months post-treatment study visit".

Serious Adverse Event Definition: is any adverse event that:

1. results in death;

2. is life-threatening (places the subject at immediate risk of death from the event as it occurred);
3. results in inpatient hospitalization or prolongation of existing hospitalization;
4. results in a persistent or significant disability/incapacity;
5. results in a congenital anomaly/birth defect; or
6. based upon appropriate medical judgment, may jeopardize the subject's health and may require medical or surgical intervention to prevent one of the other outcomes listed in this definition

Unanticipated Problems Involving Risks to Subjects or Others Definition: Unanticipated problem involving risk to subjects or others includes any incident, experience or outcome that meets all of the following criteria:

- A. unexpected (in terms of nature, severity, or frequency) given (a) the research procedures that are described in the protocol-related documents, such as the IRB-approved research protocol and informed consent document; and (b) the characteristics of the subject population being studied (note: the unfounded classification of a serious adverse event as "anticipated" constitutes serious non-compliance);
- B. definitely related or probably related to participation in the research; and
- C. suggests that the research places subjects or others at a greater risk of harm (including physical, psychological, economic, or social harm) than was previously known or recognized

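### Section 3.4 permits the PI to withdraw a participant from the study for a complication, with only an optional visit afterwards, so outcome-related loss of follow-up data is possible and avoidable

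*Combined protocol and SAP*

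**What the plan says.** Section 3.4 lists three ways out of the study. Under the first, the PI can withdraw participants on determining that "the participants have sustained any injury or complication that prevents them from continuing with the study". What ends is participation in the study. The bullet does not separate stopping treatment from stopping data collection, and it sets no timing.

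Section 7.2 describes what follows: where possible, a visit with a blood draw, questionnaires and a record of the reasons. "This is an optional visit", and "Participant will have the choice to partake any or all of the activities during withdraw visit". No later questionnaire, record review, or progression or survival follow-up is described for a withdrawn participant.

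Two other sections deal with patients who come off treatment. Section 6 says that those who develop distant metastases during induction and stop therapy "will remain on the original calendar schedule for continued follow up only". Section 5.2.7 says that if in-field toxicity delays treatment by more than 3 weeks, "the patient should be considered intolerant of protocol therapy and appropriate off-protocol therapy given"; it does not say whether study visits continue.

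Section 11 tests change in quality of life (QoL) at 36 months. It aims for 30 evaluable patients without defining the term and counts losses by reason in a CONSORT diagram. It states no analysis population, missing-data method or censoring rule.

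**The concern.** Complications of cystectomy and of chemoradiation are part of what the trial compares. If a complication can end follow-up, the chance that an outcome is observed depends on the outcome and on the arm. The arms are visibly different and the decision is at the PI's discretion.

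- **QoL** is most exposed. The test needs a 36-month value, so withdrawal at any earlier time removes the endpoint for that patient.
- **Progression-free survival (PFS)**: a patient withdrawn after treatment would presumably be censored, at a time related to prognosis. A patient withdrawn before treatment ends has no defined time zero.
- **Adverse events**: the course of the triggering event and any later events may go unrecorded.
- **Feasibility**: attrition is an Aim 2b outcome meant to inform a larger trial of the same design. PI-initiated removals would mix with losses that patients choose, and the rule could carry over into that trial.

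Data that were never collected cannot be recovered by a later analysis.

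**Working it through.** **1. The provisions side by side**

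| Situation | Where | Follow-up stated? |
|---|---|---|
| Metastases during induction, therapy stopped | Section 6 | Yes, on the original calendar |
| Prolonged toxicity, protocol therapy ended | Section 5.2.7 | Silent |
| PI withdrawal for injury or complication | Sections 3.4 and 7.2 | One optional visit |

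Two definitions decide what is lost. For PFS, Section 9.4 says "This will be measured from the date of finishing chemoradiation or radical cystectomy to the date of first documentation of progression", so time zero is the end of treatment. For safety, Section 10.2 says "all adverse events will be documented starting with the date of study enrollment and ending 30 days after" the 12-month post-treatment visit. The event that prompts a withdrawal therefore falls inside the recording window; what may be lost is what comes after it.

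**2. The plan's own figure**

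Inputs from Section 11: 50% improved after cystectomy, 60% after chemoradiation, margin 5 points, power 80%.

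n = (1.960 + 0.842)² × (0.5×0.5 + 0.6×0.4) / (0.10 + 0.05)² = 7.85 × 0.49 / 0.0225 ≈ 171 per group.

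This matches the stated 171, with one-sided alpha 2.5% and the margin taken below zero. (The printed hypotheses carry the opposite sign, which is a separate matter.) The calculation includes no dropout allowance.

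**3. Illustration at 15 per arm**

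Assumptions, none of them from the documents: w patients in an arm are withdrawn, and none of them would have improved. The observed rate is then 15p / (15 − w).

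- Cystectomy, p = 50%: 7.5/14 = 53.6%, 7.5/13 = 57.7%, 7.5/12 = 62.5%.
- Chemoradiation, p = 60%: 9/14 = 64.3%, 9/13 = 69.2%, 9/12 = 75.0%.

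Apparent difference, chemoradiation minus cystectomy, when the true difference is 10 points:

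| Withdrawn | Cystectomy only | Chemoradiation only | Same number in both |
|---|---|---|---|
| 1 | 6.4 | 14.3 | 10.7 |
| 2 | 2.3 | 19.2 | 11.5 |
| 3 | −2.5 | 25.0 | 12.5 |

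Losses in the cystectomy arm bias against chemoradiation, losses in the chemoradiation arm bias towards it, and equal losses largely cancel.

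**4. If the rule carried over to a trial of 171 per group**

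Take a true difference at the margin (45% versus 50%) and let a share d of the chemoradiation arm, all non-improvers, be withdrawn. The observed chemoradiation rate is 0.45/(1 − d) on 171(1 − d) patients. With d = 5%, 10% or 20%, one-sided type I error rises from 2.5% to 6.3%, 14.5% or 50.4% (normal approximation, unpooled variance). This is again a one-arm worst case.

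**The case against.** The strongest reply is that the rule is narrow and the loss is not certain. Section 3.4 says the PI can withdraw, and only where continuing is prevented. A reader might infer that the worst-affected patients will leave the data; the text supports only that they may. This stands.

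Other stronger readings also fail.

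- **That the triggering event is lost.** Adverse events are recorded from enrollment, reviewed monthly by the PI and reported quarterly to the safety committee.
- **That withdrawn patients vanish from PFS.** Withdrawal after treatment would presumably lead to censoring, with accrued time kept.
- **That Section 5.2.7 contradicts Section 6.** It ends protocol therapy and withdraws no one. Section 6 also refers deviations from protocol-specified treatment to a standard operating procedure that is not in the document. Silence beside an explicit rule is not a contradiction.
- **That the rule acts only after treatment.** Consent precedes TURBT and randomization, so the bullet could also apply before any arm is assigned.
- **That two withdrawals breach the margin in this pilot.** The 5-point margin belongs to the calculation for 171 per group. At 15 per arm one patient is 6.7 points, and the standard error of the difference is √(0.49/15) ≈ 18 points. A complication near treatment also does not fix QoL change three years later.

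Attrition is to be reported by arm and losses by reason, which makes the loss visible but does not restore the data.

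It could also be said that a patient who cannot continue cannot be followed. Yet Section 7.1 allows questionnaires by mail or email, Section 8 allows vitals from the medical record, Section 4 already provides for outside records, and the imaging is standard of care, as is cystoscopy in the chemoradiation arm only. Few complications would prevent follow-up of that kind.

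**Conclusion.** The concern holds as a risk that the plan permits. Sections 3.4 and 7.2 together allow follow-up to end because of a consequence of treatment, Section 6 keeps a comparable group on the calendar, and Section 11 offers nothing to offset the loss.

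The size cannot be derived from the documents, which give no withdrawal rate. The shifts of 3.6, 7.7 and 12.5 points in a 50% arm rest on assumed counts of 1, 2 and 3, on every withdrawn patient being a non-improver, and on losses in one arm only. In a pilot of 30, sampling error exceeds these shifts, so the more practical harm is to the attrition estimate and to a larger trial built on the same rule. The change is worth making because it is cheap and the data cannot be recovered afterwards.

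**What to change.** Limit the amendment to data retention.

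- **Sections 3.4 and 7.2:** after randomization, an injury or complication is not a ground for PI withdrawal from follow-up.
- **Sections 3.4, 5.2.7 and 7.2:** randomized patients who stop or do not complete protocol treatment stay on the existing follow-up calendar to month 36 unless they withdraw consent.
- **Means of collection:** questionnaires by mail or email; progression, cystectomy, survival and adverse-event data (the last within the window in Section 10.2) from medical records.

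The amendment takes no position on when treatment should stop. It costs a short text change and a small extra effort in mailing and record abstraction, with no added procedures. Some data will still be missing, so it does not replace a missing-data rule in Section 11.

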3. STUDY ENROLLMENT AND WITHDRAWAL

3.1 Inclusion Criteria:

3.1.1 Pathologically (histologically) proven diagnosis of primary carcinoma of the bladder (transitional cell cancer) within 8 weeks of registration. Operable patients whose tumors are primary carcinomas of the bladder and exhibit histologic evidence of muscularis propria invasion and are AJCC clinical stages T2-T4a, Nx or N0, M0

3.1.2 Patients without histologically or cytologically confirmed node metastases or any other metastases

3.1.3 Patients must have an adequately functioning bladder after thorough evaluation by an urologist and have undergone as thorough a transurethral resection of the bladder tumor as is judged safely possible.

3.1.4 Patients must be considered able to tolerate systemic chemotherapy combined with pelvic radiation therapy, and radical cystectomy.

3.1.5 History and physical examination including weight, performance status, and body surface area within 8 weeks prior to study registration

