3.3 Randomization Procedure

A total of 30 patients will be randomized to either chemoradiation group (n=15) or radical cystectomy (with or without neoadjuvant chemotherapy group, n=15). Permuted block randomization process through sequentially numbered, opaque sealed envelopes will be utilized in assigning participants into either radical cystectomy or chemoradiation group. All subjects will be randomized in blocks of size 2. A randomization list containing sequence numbers and treatment assignments will be prepared by the statistician and used as the sole basis for treatment assignments throughout the study.

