4.2 Baseline Visit

The potential participant will return to the urology clinic to review pathology results and treatment options within 4 weeks of TURBT. This is a routine post-TURBT follow-up visit (i.e. baseline visit). If the potential participant is deemed eligible for both radical cystectomy and chemoradiation by the treating urologist, the potential participant will then be randomized either to radical cystectomy arm or chemoradiation arm.

Each participant will be assigned a unique subject identifier (subject ID) that has no meaning external to the study database. The participant identifiers will be further masked and password protected, and stored only on a secure server behind a "firewall". Only authorized research study members will have access to these identifiers. A research study file will be kept for each participant accrued. This file will include the participant's consent, the assigned unique subject identifier, and copies of relevant source documents. All participant records will be securely stored in the Urology research offices at the MARC. A data entry system will be prepared in RedCap for the study. Both the subject identifier, sequence number, and the treatment assignment for each patient will be entered into the database together with clinical outcome data collected across visits.

During this visit, the participant will complete a study questionnaire packet, which may include and not limited to demographics, medical history; and study questionnaires *such as* EORTC QLQ C30 and FACT-BI. In the interest of time, the study questionnaire packet may also be completed at participant's home and return to the study team via mail or email (per participant preference). Study team member will strongly encourage participant to complete the study questionnaire at

the time of baseline visit. If the participant completes the questionnaires from home, a study team member may follow-up with the participant over the phone, if the completed questionnaires are not received within a week of the visit. Two tubes (~ 10 mL or 2 teaspoons each) of research blood will also be drawn. Study team member or clinic staff will record participant's height, weight, and vital signs. At the completion of the baseline measurements, each participant will be randomized to either "Radical Cystectomy" or "Chemoradiation" following a process through sequentially numbered, opaque sealed envelopes by an authorized research study member.

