8.2 CHEMORADIATION ARM

	Initial Visit	Pre-Treatment (tx) TURBT	Baseline	Treatment Period: Chemoradiation	Post-Induction Response Evaluation with Cystoscopy and biopsy (3-4 weeks following Induction Chemoradiotherapy) and second phase of treatment**	Post-tx 3 mon f/u ± 1 mon	Post-tx 6 mon f/u ± 1 mon	Post-tx 9 mon f/u ± 1 mon	Post-tx 12 mon f/u ± 1 mon	Post-tx 18 mon f/u ± 1 mon	Post-tx 24 mon f/u ± 1 mon	Post-tx 30 mon f/u ± 1 mon	Post-tx 36 mon f/u ± 1 mon (end of study visit??)			
Study eligibility	X		X													
Informed consent	X															
Assessment of AE								X	X	X	X	X	X	X	X	X
SOC Image studies (X-Ray, CT, and/or MRI)			X					X	X	X	X	X	X	X	X	X
Radiation & Medical Oncology Consults (SOC)			X													
Research blood sample			X					X	X	X	X	X	X	X	X	X
Ht, Wt, and Vitals [#]			X					X	X	X	X	X	X	X	X	X
Research Study Questionnaires			X					X	X	X	X	X*	X*	X*	X*	X*

Note:

SOC = Standard of Care

information may be extracted from EMR

*Research study questionnaire may be emailed or mailed per patient's stated preference

** Post-treatment cystoscopy is SOC for chemoradiation patients ONLY

**Pending on the results of post-induction TURBT and response evaluation, participant may receive further treatments. Details on the second phase of treatment are listed in Section 6 and Study Synopsis.

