10.4 Assuring Compliance with Protocol and Data Accuracy

As with all studies conducted at CTRC, the PI has ultimate responsibility for ensuring protocol compliance, data accuracy/integrity and responding to recommendations that emanate from monitoring activities. Source verification of data will be performed every twelve week. Protocol compliance, data accuracy and reporting of events is further ensured by an annual audit conducted by the Data Safety Officer, whose audit report is shared with the PI, the research team, and will be reviewed by the CTRC DSMC.

11. STATISTICAL CONSIDERATIONS:

For this pilot non-inferiority study, we aim to randomize **30** evaluable patients (**radical cystectomy: n=15, chemoradiation: n=15**).

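### The withdrawal rule for patients found unsuitable for chemoradiation can act after randomisation, and mainly in one arm, and nothing in the plan keeps these patients in the analysis

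*Combined protocol and SAP*

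**What the plan says.** **Entry and allocation.** Section 3.1.4 makes tolerance of both treatments an entry criterion: "Patients must be considered able to tolerate systemic chemotherapy combined with pelvic radiation therapy, and radical cystectomy". Section 4.2 leaves that judgement to one clinician, "If the potential participant is deemed eligible for both radical cystectomy and chemoradiation by the treating urologist", and fixes the moment of allocation: "At the completion of the baseline measurements, each participant will be randomized to either" arm. Neither section makes a radiation or medical oncology consult a precondition.

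**Withdrawal.** Section 3.4 allows the PI to withdraw a participant who is "considered not a candidate for chemoradiation treatment after radiation and/or medical oncology consult". It names no arm and no time point. What it describes is leaving the study, not a change of treatment. Section 7.2 then offers one optional visit, at which reasons are asked and recorded. No later outcome follow-up is described.

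**Where the consult is scheduled.** Calendar 8.2 (chemoradiation) has a row for the radiation and medical oncology consults, with a single mark that appears to sit under Baseline. Calendar 8.1 (cystectomy) has no such row. Section 5.1 mentions a medical oncologist in the cystectomy arm only for the choice of neoadjuvant regimen.

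**Analysis.** Section 3.3 says "A total of 30 patients will be randomized", 15 per arm. Section 11 aims to randomise 30 "evaluable patients" and does not define the term. No analysis set, replacement rule or missing-outcome rule is given. Section 9.4 starts the PFS clock when chemoradiation or cystectomy is finished. Section 9.1 reports attrition and compliance with randomisation by arm, and Section 11 plans a CONSORT diagram.

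**The concern.** Suitability for chemoradiation is judged by the urologist before allocation and may be judged again by an oncologist, but the second judgement is scheduled in one arm only. A cystectomy patient who would have failed the same consult is unlikely to be identified and stays in. A chemoradiation patient who fails it can leave the study.

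If the patients who leave are less fit and do worse, the chemoradiation arm is improved by selection and not by treatment. Section 11 plans formal non-inferiority assessments of quality of life, PFS and bladder-intact survival, and this selection pushes all three towards non-inferiority. These are also patients whom Aim 2b exists to count, because they bear directly on whether a larger trial could deliver its assigned treatments.

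**Working it through.** **1. The plan's own figure.** Section 11 assumes improvement in 50% (cystectomy) and 60% (chemoradiation), a 5-point margin, 80% power and alpha 5%.

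n per group = (1.960 + 0.842)² × (0.60×0.40 + 0.50×0.50) / (0.10 + 0.05)² = 7.849 × 0.49 / 0.0225 = 170.9, so 171.

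This reproduces the stated figure at one-sided alpha 0.025; one-sided 0.05 gives 135. The 171 is the size of an adequately powered trial. The pilot's 15 per arm has no calculation behind it. The 60% rate and the 5-point margin are used below for scale.

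**2. The same unsuitable patient in each arm.**

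| Step | Chemoradiation | Cystectomy |
|---|---|---|
| Fitness for both treatments judged before allocation | Urologist (4.2) | Urologist (4.2) |
| Consult on chemoradiation candidacy | Scheduled (8.2) | Not scheduled (8.1); possible medical oncology contact about neoadjuvant treatment (5.1) |
| Withdrawal under 3.4 | Can be triggered | Only incidentally |
| Follow-up after withdrawal | Optional visit (7.2) | Optional visit (7.2) |
| PFS start | None if chemoradiation is never finished, unless a later cystectomy is counted (9.4) | End of surgery (9.4) |

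Section 6 gives a contrast. Patients who develop metastases during induction and stop therapy stay on the calendar for follow-up. The protocol can retain untreated patients, but 3.4 does not say so.

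**3. Effect of losing k of 15 patients from the chemoradiation arm.** Let p = 0.60 (9 of 15, the Section 11 assumption), w = k/15, and q = the improvement rate of those removed. The documents give neither k nor q, so both are assumptions.

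Shift = (p − wq)/(1 − w) − p

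| k | w | q = 0 | q = 0.25 | q = 0.60 |
|---|---|---|---|---|
| 1 | 6.7% | 9/14 = 64.3% (+4.3 points) | 62.5% (+2.5) | 60% (0) |
| 2 | 13.3% | 9/13 = 69.2% (+9.2) | 65.4% (+5.4) | 60% (0) |
| 3 | 20.0% | 9/12 = 75.0% (+15.0) | 68.8% (+8.8) | 60% (0) |

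The q = 0 column is the extreme case. The last column shows no bias when those removed resemble the rest.

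**4. Chance that it happens at all.** If a share d of patients is found unsuitable at consult, the chance of at least one among 15 is 1 − (1 − d)^15. For d = 5%, 10% and 20% (assumed) this is 54%, 79% and 96%.

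**The case against.** **Timing and arm.** A reader might take 3.4 to be a post-randomisation rule for the chemoradiation arm alone. The text does not say that. Consent precedes TURBT and allocation, so a consented participant could be withdrawn before the envelope is opened. The consult's mark appears to fall under Baseline, and 4.2 randomises only after the baseline measurements. A cystectomy patient may also see a medical oncologist. All of this stands. What remains is that nothing requires the consult before allocation and only one calendar contains it.

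**Exclusion and replacement.** A reader might infer that withdrawn patients will be dropped or replaced. Section 11 speaks of randomising 30 such patients, so both sections count randomised patients, and neither mentions replacement. Exclusion is left open, not prescribed.

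**Hidden losses.** A reader might say that the plan conceals how many patients could not receive chemoradiation. It does not: 7.2 records reasons, 9.1 reports attrition by arm, and the CONSORT diagram shows losses by reason. These reports count the patients but do not return their outcomes to the comparison.

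**Importance in a pilot.** With 15 per arm the standard error of 60% v 50% is √(0.24/15 + 0.25/15) = 18 points, larger than any shift in step 3. The efficacy comparison will be weak in any case. That limits the consequence for this trial's inference. It does not justify a selective loss, in a design meant to be carried into a larger trial, that the protocol could avoid.

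**Conclusion.** The concern holds in a limited form. Read together, 3.4, 4.2 and the two calendars allow a withdrawal that follows allocation and falls mainly on the chemoradiation arm. Sections 7.2, 9.4 and 11 leave such a patient without assured follow-up, a PFS start date or a named analysis set. If those patients have a worse prognosis, the effect favours non-inferiority.

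The size cannot be derived from the documents. The shift from 60% to between 64% and 75% assumes one to three losses, none of whom would have improved. At a 25% improvement rate among those lost, the shifts are 2.5 to 8.8 points; at the arm's own rate they are zero.

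It would be tempting to add a PFS scenario. With 20% unfit and 3-year PFS of 30% v 60% in the fit, cystectomy would show 0.8×0.60 + 0.2×0.30 = 54% against 60%, and that 6-point gap could be set beside the 5-point margin. The documents do not support this: every input is assumed, and the margin is stated for quality of life, not PFS.

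**What to change.** 1. In 3.4 and 7.2, state that a participant found after randomisation not to be a candidate for chemoradiation stays in outcome follow-up unless consent is withdrawn. The treatment that the patient then receives is a clinical matter which this change does not touch.
2. In Section 11, name the main analysis as all randomised patients in the arm assigned. Replace 'evaluable' by 'randomised' and state that patients are not replaced.
3. In 9.4, time PFS from randomisation in both arms, so that a patient who never finishes treatment still has a start date.
4. Report the number found unsuitable at consult as an Aim 2b result, separately from other attrition.
5. Reconcile 3.4, 4.2, 8.1 and 8.2 on whether the consult precedes randomisation and to whom it applies.

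The cost is wording in these sections plus continued follow-up of a few untreated patients. Some chemoradiation-arm patients will be analysed without having received it. In a non-inferiority comparison that dilution can itself draw the arms together, so a supportive summary of patients who received their assigned treatment is worth adding. The change should be made before such withdrawals occur, because outcomes not collected after withdrawal may not be recoverable later.
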